1. SYNOPSIS

Title	Optimizing post-allogeneic hematopoietic cell transplant outcomes for lymphoma using ibrutinib
Background	Given the emergence of non-hematopoietic cell transplant (HCT) options for this patient population, and the relatively high risk of non-relapse mortality (NRM) associated with HCT, only patients with advanced disease (and thus at a high risk for post HCT relapse) are typically referred for transplant. HCT has become increasingly safe, but relapse post HCT and immune mediated disorders after HCT (viz. graft-versus-host disease, GVHD) remain the main obstacles to successful outcome. Maintaining control of the neoplasm in the early post HCT period until GVT is established should lead to improved outcomes.
Primary Objective	To study the use of ibrutinib starting between days 60 and day 90 after allogeneic HCT until 12 months post HCT to improve the PFS at 12 months post HCT by 25% compared to historical controls in patients with MCL and CLL.
Secondary Objective:	
 • CLL/MCL cohort (Cohort A) 
 ○ To increase the incidence of successful outcome (defined as lack of requirement of second line therapy for acute GVHD, lack of NIH severe chronic GVHD, lack of progression or relapse of CLL/MCL, lack of death from disease or non-relapse causes) to at least 60% at 1 y post HCT. • To study the safety and tolerability of ibrutinib post HCT in patients enrolled on cohort A (CLL and MCL) and cohort B (follicular center cell lymphoma [FL] and Hodgkin lymphoma [HL]). • Acute GVHD 
 ○ To study the incidence of grade 3-4 acute GVHD in the first 6 months post HCT in patients with non-Hodgkin and Hodgkin lymphoma (cohort A and B combined). ○ To study the incidence of second line therapy (systemic only) for acute GVHD in the first 6 months post HCT in patients with non-Hodgkin and Hodgkin lymphoma (cohort A and B combined). ○ To study the incidence of recurrent acute GVHD in the first 6 months post HCT in patients with non-Hodgkin and Hodgkin lymphoma (cohort A and B combined). • Chronic GVHD 
 ○ To study the incidence and severity of chronic GVHD in the first 12 months post HCT in patients with non-Hodgkin and Hodgkin lymphoma (cohort A and B combined). ○ To study the incidence of lung involvement with GVHD in the first 12 months post HCT in patients with non-Hodgkin and Hodgkin lymphoma (cohort A and B combined). ○ To study the incidence of sclerotic skin chronic GVHD in the first 12 months post HCT in patients with non-Hodgkin and Hodgkin lymphoma (cohort A and B combined) • To study the incidence of infectious deaths not related to GVHD in patients with non-Hodgkin and Hodgkin lymphoma (cohort A and B combined). • Correlative studies 
 ○ Cohort A: To study the association of MRD as detected by IgH sequencing prior to starting ibrutinib and compare to post ibrutinib at month 6, 9 and 12

	
after HCT. In addition to study the impact of onset of new acute or chronic GVHD on MRD.
 
 ○ Cohort A: To study the association of T-cell clonality by T cell receptor (TCR) Vb sequencing prior to starting ibrutinib and compare to post ibrutinib at month 6, 9 and 12 after HCT. In addition to study the impact of onset of new acute or chronic GVHD on TCR sequencing. ○ Cohort A: To study the association of B cell receptor signaling pathways and immune function with response by single cell mass cytometry prior to starting ibrutinib and compare to post ibrutinib at month 6, 9 and 12 after HCT. ○ Cohort A: To study the association of single cell mass cytometry that investigates B cell receptor signaling and its association with new acute or chronic GVHD on BCR signaling.

Inclusion criteria
	
 ● Pre-SCT 
 ○ Adult (≥ 18 y) patients undergoing their first T cell replete allo-HCT chronic lymphocytic leukemia (CLL), Hodgkin Lymphoma (HL), or the following subtypes of Non-Hodgkin lymphoma: Mantle cell lymphoma (MCL) and follicular center cell lymphoma (FL) ○ Meeting institutional criteria for allo-HCT. Ejection fraction by echocardiogram or MUGA >40%, pulmonary function test with adjusted DLCO ≥ 60% ○ Matched (8/8) or mismatched (7/8) related, unrelated HCT ○ Stem cell source: bone marrow, peripheral blood stem cell ○ Disease criteria: 
 Cohort A: CLL 
 -Disease burden: lymph node size <5cm and/or extra-nodal involvement <5 cm AND -17 p deletion (detected by any assay) (≥20% of cells involved if assay is conventional cytogenetics or FISH) or NOTCH mutation at any time point during disease course. Patient should have received at least 1 line of therapy. Prior ibrutinib therapy is permitted. OR -Relapsed/refractory CLL ≥ 2 lines of therapy. Prior ibrutinib therapy is permitted MCL 
 -Disease burden: lymph node size <5 cm and/or extra-nodal involvement < 5 cm AND --Relapsed/refractory MCL ≥ 1 line of therapy. Prior ibrutinib therapy is permitted. Prior autologous HCT is permitted OR -MCL blastoid variant in CR1 or MCL being considered for allo HCT in CR1

	
Cohort B:
 
FL
 
 - Disease burden: lymph node size <5cm and/or extra-nodal involvement <5 cm 
AND
 
 -Relapsed/refractory FL ≥ 2 lines of therapy. Prior ibrutinib therapy is permitted 
HD
 
 - Disease burden: lymph node size <5cm and/or extra-nodal involvement <5 cm 
AND
 
 -Relapsed/refractory HD ≥ 2 lines of therapy 
 • Prior to administration of ibrutinib (day 60 to day 90 post HCT) 
 ○ KPS ≥ 60% ○ Engraftment of neutrophils (ANC ≥ 1.0 X10⁹/L) for 3 days without g-csf support ○ Platelets ≥100,000/mm³ or ≥50,000/mm³ if bone marrow involvement independent of transfusion support in either situation ○ GFR ≥ 30 ml/min ○ LFTs (ALT and AST) ≤ 3 X ULN; total bilirubin ≤ 1.5 mg/dL XULN unless bilirubin rise is due to Gilbert's syndrome or of non-hepatic origin ○ Predominant donor chimerisms of ≥ 51% as measured by CD3 and CD33 (or other myeloid marker)

Exclusion criteria
	
 • Pre-SCT 
 ○ Progression of CLL or MCL or FL or HD at time of transplant ○ Use of Coumadin (warfarin) or other vitamin-K antagonists for anticoagulation. Non-coumadin anticoagulation is permitted. ○ Active uncontrolled CNS involvement ○ Active uncontrolled bacterial or invasive fungal infections ○ History of malignancy other than the underlying disease unless treated with a curative intent and/or no evidence of disease for at least 3 y OR expected to be cured with SCT ○ Planned use of post-HCT cyclophosphamide for GVHD prophylaxis ○ Anticipated planned donor lymphocyte infusion in the first 3 months post-SCT ○ T cell depleted HCT ○ Umbilical cord HCT ○ History of stroke or intracranial hemorrhage within 6 months prior to enrollment. ○ Clinically significant cardiovascular disease such as uncontrolled or symptomatic arrhythmias, congestive heart failure, or myocardial infarction within 6 months of Screening, or any Class 3 (moderate) or Class 4 (severe) cardiac disease as defined by the New York Heart Association Functional Classification.

	
 ● Prior to administration of ibrutinib (day 60 to day 90 post SCT) 
 ○ In the critical care unit, or use of mechanical ventilation or use of renal replacement therapy at any time post SCT and prior to administration of ibrutinib ○ Active uncontrolled stage 3-4 acute GI GVHD prior to administration of ibrutinib ○ Active uncontrolled stage 4 acute liver GVHD prior to administration of ibrutinib ○ Evidence of progressive disease as compared to pre-SCT (persistence of disease is permitted) ○ Anticipated planned donor lymphocyte infusion in the first 3 months post-SCT ○ Active uncontrolled bacterial or invasive fungal infections ○ Prednisone equivalent of >2mg/kg for treatment of GVHD prior to administration of ibrutinib ○ Use of second line systemic therapy for treatment of acute GVHD prior to administration of ibrutinib ○ Any life-threatening illness, medical condition, or organ system dysfunction which, in the investigator's opinion, could compromise the subject's safety, interfere with the absorption or metabolism of ibrutinib capsules, or put the study outcomes at undue risk including the presence of chronic/active HBV and HBC infections and Child-Pugh Class C. ○ Major surgery or a wound that has not fully healed within 4 weeks of starting ibrutinib ○ Requires anticoagulation with warfarin or equivalent vitamin K antagonists (e.g., phenprocoumon). ○ Requires chronic treatment with strong CYP3A inhibitors ○ Vaccinated with live, attenuated vaccines within 4 weeks of starting ibrutinib

Study schedule
	
Patients will start ibrutinib at a dose of 420 mg by mouth once a day between day 60-90 post HCT and continue until 1 y post HCT.
 
Patients on azoles will start ibrutinib at a dose of 140 mg by mouth once a day between day 60-90 post HCT and continue until 1 year post HCT.
 
Patients using Posaconazole as outlined in section 11.2 will start ibrutinib at a dose of 70 mg by mouth once a day between day 60-90 post HCT and continue until 1 year post HCT.

2. INTRODUCTION

Chronic lymphocytic leukemia (CLL) and mantle cell lymphoma (MCL) represent the heterogeneity of B-cell Non-Hodgkin lymphoma, with varying natural histories and pathobiology. Interestingly, targeting the B-cell receptor signaling pathway using ibrutinib, a Bruton tyrosine kinase inhibitor, favorably impacts both of these diseases¹⁻⁶. Despite advances in both cytotoxic and immunotherapeutic approaches, an allogeneic hematopoietic cell transplant (HCT) is the only curative option⁷⁻¹¹. This is primarily mediated by graft-versus-tumor (GVT) effect¹²⁻¹⁴. Given the emergence of non-HCT options for this patient population, and the relatively high risk of non-relapse mortality (NRM) associated with HCT,

only patients with advanced disease (and thus at a high risk for post HCT relapse) are typically referred for transplant. HCT has become increasingly safe, but *relapse post HCT* and *immune mediated disorders after HCT* (viz. graft-versus-host disease, GVHD) remain the main obstacles to successful outcome. Maintaining control of the neoplasm in the early post HCT period until GVT is established should lead to improved outcomes. Use of conventional cytotoxic agents is not practical in the early post HCT period.

We propose the following primary objective: to study the use of ibrutinib starting between day 60 and day 90 after HCT until 12 months post HCT to improve the progression-free survival (PFS) at 12 months post HCT by 25% compared to historical controls in patients with of CLL and MCL (cohort A).

GVHD is a complex immune phenomenon that is classically defined as acute and chronic and affects a variety of organ systems. The initial phase of GVHD is primarily T cell mediated. Figure 1 shows the various roles of the normal B cell. Adequate pre-clinical and clinical data shows that B-cell dysfunction contributes to chronic GVHD¹⁵⁻²⁰. Pre-clinical data shows that part of this dysfunction is due to hyper-responsiveness of the B-cell receptor (BCR), which can be abrogated by disrupting the signaling downstream of the BCR²¹. Thus, it is conceivable that using ibrutinib post HCT may not only lead to effective tumor control but down modulate GVHD. Based on these data, ibrutinib was studied as a single agent for established chronic GVHD

[figure not shown]

Figure 1: The various functions of the normal B cell in the setting of HCT

(NCT02195869) and approved for chronic GVHD after failure of one or more lines of systemic therapy. It is likely that the effect on GVHD may be prevalent in patients with other lymphomas as well.

Thus, in the secondary objective: *we propose to study the safety, tolerability and impact on acute and chronic GVHD. This aim will encompass diagnoses other than CLL and MCL and will include follicular center cell lymphoma (FL) and Hodgkin lymphoma (HL) (Cohort B).*

3. PRIMARY OBJECTIVE

To study the use of ibrutinib starting between day 60 and day 90 after allogeneic HCT until 12 months post HCT to improve the PFS at 12 months post HCT by 25% compared to historical controls. The sample size is designed to address this primary endpoint.

4. SECONDARY AND EXPLORATORY OBJECTIVES

- CLL/MCL cohort (Cohort A)
 - To increase the incidence of successful outcome (defined as lack of requirement of second line therapy for acute GVHD, lack of NIH severe chronic GVHD, lack of progression or relapse of CLL/MCL, lack of death from disease or non-relapse causes) to at least 60% at 1 year post HCT.

- To study the safety and tolerability of ibrutinib post HCT in patients with non-Hodgkin lymphoma (NHL) and HL (cohort A and B combined)
- Acute GVHD
 - To study the incidence of grade 3-4 acute GVHD in the first 6 months post HCT in patients with NHL and HL (cohort A and B combined)
 - To study the incidence of second line therapy (systemic only) for acute GVHD in the first 6 months post HCT in patients with NHL and HL (cohort A and B combined)
 - To study the incidence of recurrent acute GVHD in the first 6 months post HCT in patients with NHL and HL (cohort A and B combined)
- Chronic GVHD
 - To study the incidence and severity of chronic GVHD in the first 12 months post HCT in patients with NHL and HL (cohort A and B combined)
 - To study the incidence of lung involvement with GVHD in the first 12 months post HCT in patients with NHL and HL (cohort A and B combined)
 - To study the incidence of sclerotic skin chronic GVHD in the first 12 months post HCT in patients with NHL and HL (cohort A and B combined)
- To study the incidence of infectious deaths not related to GVHD in patients with non-Hodgkin and Hodgkin lymphoma (cohort A and B combined)
- Correlative studies
 - Cohort A: To study the association of MRD as detected by IgH sequencing prior to starting ibrutinib and compare to post ibrutinib at month 6, 9 and 12 after HCT. In addition to study the impact of onset of new acute or chronic GVHD on MRD.
 - Cohort A: To study the association of T-cell clonality by T cell receptor (TCR) Vb sequencing prior to starting ibrutinib and compare to post ibrutinib at month 6, 9 and 12 after HCT. In addition to study the impact of onset of new acute or chronic GVHD on TCR sequencing.
 - Cohort A: To study the association of B cell receptor signaling pathways and immune function with response by single cell mass cytometry prior to starting ibrutinib and compare to post ibrutinib at month 6, 9 and 12 after HCT.
 - Cohort A: To study the association of single cell mass cytometry that investigates B cell receptor signaling and its association with new acute or chronic GVHD on BCR signaling.

5. SCIENTIFIC RATIONALE

5.1 Rationale for Use of Ibrutinib Post HCT-Control of Neoplasm

Ibrutinib is a first-in-class, potent, orally administered covalently-binding inhibitor of Bruton's tyrosine kinase (BTK). Inhibition of BTK blocks downstream BCR signaling pathways and thus

prevents B-cell proliferation. In vitro, ibrutinib inhibits purified BTK and selected members of the kinase family with 10-fold specificity compared with non-BTK kinases. The phosphorylation and activation of BTK by Src family protein kinases (e.g.: LYN, SYK) leads to PLC γ 2 phosphorylation, calcium mobilization and activation of downstream pathways (AKT, MAP kinase, NF κ B) that leads to changes that promote cell differentiation, proliferation and survival^{22,23}. Ibrutinib covalently binds to a cysteine residue in the BTK active site and irreversibly inhibits BCR signaling downstream of BTK. In vivo, ibrutinib reduces the phosphorylation of BTK, PLC γ 2, AKT, and ERK pathways²⁴. Similar effects were observed in vitro in MCL

[figure not shown]

Figure 2: Outcome of 46 patients with CLL/MCL after first HCT at Vanderbilt University Medical Center. Cumulative incidence of failure by 1 y post HCT (defined as requirement of second line therapy of acute GVHD, development of NIH moderate to severe chronic GVHD, death due to relapse/progression, death due to non-relapse causes) was 50%.

cells. NF κ B downregulation was not limited to peripheral blood but was also noted in bone marrow and lymph nodes. BTK is a member of the Tec kinase family that transmits signals from various cell surface receptors most

prominently from the BCR. BTK plays a role in the intermediate stages of BCR signaling cascade and is commonly overexpressed in MCL and CLL²⁵. Ibrutinib (IMBRUVICA™) is approved by the U.S. Food and Drug Administration (FDA) for the treatment of patients with chronic lymphocytic leukemia (CLL) or mantle cell lymphoma (MCL) who have received at least one prior therapy and in CLL patients with del 17. In January 2015, it was approved for Waldenström’s macroglobulinemia. In August 2017, it was approved for chronic GVHD after failure of one or more lines of systemic therapy. Patients undergoing HCT remain at a high risk of relapse post-HCT. Continued post-HCT treatment may be of benefit until GVT has had a chance to eliminate the neoplasm. Thus, patients on the proposed study will start ibrutinib post-HCT, to see if post-HCT use can decrease the risk of relapse or progression. For the most comprehensive nonclinical and clinical information regarding ibrutinib background, safety, efficacy, and in vitro and in vivo preclinical activity and toxicology of ibrutinib, refer to the latest version of the ibrutinib USPI.

5.2 Rationale for Use of Ibrutinib Post HCT-Impact on GVHD Biology

Ibrutinib is a first-in-class, potent, orally administered covalently-binding inhibitor of Bruton’s tyrosine kinase (BTK) and may be a more potent B cell malignancy drug than rituximab^{4,26}. BTK is a critical intermediate in BCR signaling²⁷. It is a non-receptor tyrosine kinase belonging to the Tec family of kinases (TKs), and critical for B cell processes effected by the BCR²⁷. Individuals who lack functioning BTK lack circulating B cells and are unable to produce immunoglobulins or mount humoral immune responses²⁸. BCR ligation leads to BTK activation which subsequently phosphorylates phospholipase C γ 2 (PLC γ 2) triggering a series of downstream events including transcriptional regulation involving NF- κ B and NFAT²⁷. BTK appears to regulate B cell survival by triggering the classical pathway in response to BAFF under both BCR and BAFF-R signaling²⁹. Ibrutinib is also an irreversible inhibitor of interleukin-2 inducible kinase (ITK). ITK is involved in proximal T-cell receptor (TCR) signaling which activates the signaling cascade that includes NFAT, NF κ B, and MAPK pathways resulting in T cell activation. ITK has a dominant role in the activation of Th2 cells, but not in Th1 cells.

GVHD is a complex immune phenomenon that is classically defined as acute and chronic and affects a

variety of organ systems. The initial phase of GVHD is primarily T cell mediated. Figure 1 shows the various roles of the normal B cell. Adequate pre-clinical and clinical data shows that B-cell dysfunction contributes to chronic GVHD^{15;17;19;30;31}. Pre-clinical data shows that part of this dysfunction is due to hyper-responsiveness of the B-cell receptor (BCR), which can be abrogated by disrupting the signaling downstream of the BCR²¹.

Thus, it is conceivable that using ibrutinib post HCT, may not only lead to effective tumor control but may down modulate GVHD as well. Ibrutinib was studied as a single agent for established chronic GVHD (NCT02195869) and has been approved by the FDA for treatment of chronic GVHD after failure of 1 or more systemic therapies. However, the relationship between early ibrutinib use post-transplantation and the incidence (and severity of) GVHD development has not been examined and may impact NRM. The RP2D in patients with established chronic GVHD is 420 mg.

5.3 Rationale for Duration of Ibrutinib Post HCT

Although the incidence of complete response (CR) in MCL and CLL in the non-transplant population is low^{1;4-6}, the incidence of CR post HCT is higher. Also, it is expected that GVT will be the final pathway to effect cure. The role of ibrutinib post HCT is to maintain effective tumor control until GVT is established. In the absence of clinical GVHD, immunosuppressive therapy (IST) is tapered starting at day 100, with a goal of IST cessation by 6 months post HCT. Thus, stopping ibrutinib at 12 months post HCT in patients who have achieved a CR reflects a time point at which one would expect GVT to be established. Also, it is expected that ibrutinib may down modulate chronic GVHD. It is not clear if ibrutinib can facilitate transplantation tolerance. We hypothesize that using ibrutinib starting at day 60-90 post HCT until 12 months post HCT, will increase the incidence of a successful outcome by 25% compared to historical controls. The correlative studies will address molecular monitoring of disease (in cohort A), mechanisms of relapse of disease and development (or lack of) GVHD.

5.4 Rationale for Composite Secondary Endpoint

Typically, IST is continued until day 100 post HCT followed by a planned taper and attempts at IST cessation by day 180-day 270. Recurrent acute GVHD, grade 3-4 acute GVHD and severe chronic GVHD (as defined by NIH criteria)³² represents the cohort of patients most likely to experience high risk of NRM³³⁻³⁵. Patients at high risk of early post HCT relapse or persistence of disease at day 30 post HCT are often managed by forced IST tapers to elicit GVT. This often increases the risk of early GVHD and sets the stage for chronic GVHD. Although the *primary objective* of the proposed study is improvement in PFS in patients with MCL and CLL, this endpoint is intertwined with risk of NRM from GVHD. The sample size is designed to address this primary objective and stopping rules have been developed to ensure safety. In addition, we propose a composite secondary endpoint. A successful outcome post HCT is defined as lack of recurrence of the underlying disease with achievement of transplantation immunological tolerance, typically documented as cessation of all immunosuppression without active GVHD and functional immune reconstitution. As these endpoints can be distant, we propose a *composite secondary endpoint to be measured at 12 months post HCT* with success being defined as lack of progression or recurrence of disease, lack of second line therapy for acute GVHD, lack of NIH severe chronic GVHD and lack of death. In review of our single center data (2002-2013) of 46 patients with CLL (N=31) and MCL (N=15) undergoing their first HCT, the cumulative incidence of success at 1 y post HCT (lack of relapse or progression, lack of second line therapy for acute GVHD, lack of NIH moderate to severe chronic GVHD) was only 50% (Figure 2) (unpublished institutional data).

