 - Signed and completed Eligibility Checklist. **To be eligible for registration to the study, the participant must meet each inclusion and exclusion criterion listed in the eligibility checklist.**

Note: All study documents should be received 24-48 hours prior to the patient's anticipated start date. Same day treatment registrations will only be accepted with prior notice and discussion with the Coordinating Center. Please email the Coordinating Center if enrollment is needed sooner.

Upon satisfactory review of eligibility documents submitted, the Coordinating Center will approve enrollment and issue a subject ID number if one was not issued at screening. Once registration/enrollment confirmation from Coordinating Center is received, proceed with protocol procedures.

Please contact the assigned Study Contact with any questions regarding this process. You can also reach out to your assigned CRA once the study is activated.

The VICC Coordinating Center will assign Subject ID numbers to all patients whose eligibility has been confirmed. Only patients deemed eligible will be registered to investigational treatment.

Sequence/study ID numbers will not be re-used if a patient screen fails. Following registration, eligible participants should begin study treatment consistent with the protocol no later than [XXX days/weeks] after registration/enrollment by the VICC Coordinating Center. If a participant does not receive protocol therapy following registration within the allowed time period, the participant's registration on the study will be canceled. The Study Contact should be notified of cancellations as soon as possible. Patients being re-screened will need to consent to repeated procedures. As such, the Coordinating Center will require a new, signed Informed Consent document.

Issues that would cause treatment delays should be discussed with the Protocol Chair. Any requests for eligibility exceptions and/or deviations must be approved in writing by the Protocol Chair and the VICC DSMC.

As is generally accepted, standard of care procedures performed prior to consent, but within the protocol defined screening window for each assessment, can be used for study purposes. All research-only procedures must be performed after patient consent.

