- Standard of care: Following should be done **weekly for 4 weeks and then monthly until 6 months post HCT and then at month 9** after starting ibrutinib
 - Hematology
 - Hematology parameters performed at local laboratory will include at a minimum a complete blood count: white blood cells, red blood cells, hemoglobin, hematocrit, platelets, and absolute neutrophil count.
 - Chemistry
 - Serum chemistry parameters performed at local laboratory will include at a minimum: creatinine, AST, ALT, alkaline phosphatase, and total bilirubin.

- Standard of care: To be done at month 6 and 9 post-HCT Peripheral blood T-cell, B-cell and NK cell subsets (CD3+, CD4+, CD8+, CD19+, CD16/56+)
- Research: Following should be done **at month 6 and 9 after** starting ibrutinib
 - A peripheral blood sample on all patients should be sent for Immunoseq for T-cell receptor. See the Laboratory Manual for sample acquisition, processing and shipping logistics.
 - Research: a peripheral blood sample will be collected for CyTOF analyses. See the Laboratory Manual for detailed instruction on collection, processing and shipping.
- Toxicity assessment:
 - Research: Toxicity assessment will be done on first day of administration of ibrutinib to establish post-HCT baseline.
 - Research: Toxicity assessment will be done weekly after the start of ibrutinib until day 100 post HCT or at least 4 weeks post-ibrutinib (whichever is longer)
 - Research: Toxicity assessment will be done monthly until 12 months post HCT. Month 7,8, 10, and 11 toxicity assessment can be done telephonically if a patient is unable to travel back to the transplant center. A final toxicity assessment will be conducted 12 months post HCT.
 - Concomitant medication use will be recorded at month 6 and month 9
- Acute GVHD assessment
 - Standard of care: weekly assessment of acute GVHD until day 100 (+/- 1 week) post HCT or at least 4 weeks post-ibrutinib (whichever is longer). See the Clinical Assessment Manual for acute GVHD assessment forms
- Chronic GVHD assessment
 - Standard of care: Assessment at month 6 and 9 post HCT. NIH 2015 diagnosis and scoring forms will be used. See the Clinical Assessment Manual for chronic GVHD assessment forms

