12. Weekly assessment of acute GVHD: post-ibrutinib, weekly for 4 weeks or until day 100 post HCT whichever is later. See the Clinical Assessment Manual.
13. Please ensure eligibility checklist is complete and has been reviewed by coordinating center prior to the administration of ibrutinib between day 60 and 90 post HCT. All SOC and research studies must be done within 2 weeks of starting ibrutinib.
14. Toxicity assessment should be at the transplant center 30 days after cessation of study drug in addition to end of study.
15. The End of Study visit should be completed even for patients who withdraw from study without initiating Ibrutinib

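### The composite target of at least 60% success counts only severe chronic GVHD as failure, while the only historical rate (50% of 46) counts moderate to severe and is defined two ways, so a result near 60% may not mean improvement

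*Combined protocol and SAP*

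**What the plan says.** Section 4 (and the synopsis) defines success for cohort A through "lack of requirement of second line therapy for acute GVHD, lack of NIH severe chronic GVHD", together with no progression or relapse and "lack of death from disease or non-relapse causes) to at least 60% at 1 year post HCT". Section 5.4 repeats this definition, again with severe chronic GVHD only.

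Section 5.4 then reports the centre's own experience from 2002 to 2013 in 46 patients (31 CLL, 15 MCL). Success there required no relapse or progression, no second-line acute GVHD therapy and "lack of NIH moderate to severe chronic GVHD) was only 50% (Figure 2) (unpublished institutional data". Death is not listed.

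The Figure 2 caption in section 5.1 gives the complementary failure figure for the same number of patients. It counts second-line acute GVHD therapy, "development of NIH moderate to severe chronic GVHD, death due to relapse/progression, death due to non-relapse causes) was 50" percent. Relapse or progression that is not fatal is not listed.

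Section 5.3 hypothesises that ibrutinib "will increase the incidence of a successful outcome by 25% compared to historical controls". Section 24 compares only PFS with history. It gives no reference rate, test or interval for the composite.

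**The concern.** Moving from moderate-to-severe to severe-only chronic GVHD makes success easier to reach. A patient whose only event is moderate chronic GVHD failed in the historical series but succeeds in the trial. Some of the distance between 50% and 60% could therefore appear without any drug effect.

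The two descriptions of the 50% complicate this. The trial counts both death and non-fatal relapse as failures. Section 5.4 leaves out the first and the Figure 2 caption leaves out the second. If either omission is real, some historical successes would fail under the trial definition, which pulls the benchmark down and offsets part of the chronic GVHD shift.

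At stake is the reading of a named efficacy objective with a numeric target. A result near 60% could reflect the narrower criterion rather than ibrutinib. A result well above the plausible re-scored range would still be informative.

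**Working it through.** **Definitions side by side**

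| Failure component | Trial (sections 1, 4, 5.4) | History, section 5.4 text | History, Figure 2 caption |
|---|---|---|---|
| Second-line acute GVHD therapy | yes | yes | yes |
| Chronic GVHD | severe only | moderate to severe | moderate to severe |
| Relapse or progression, non-fatal | yes | yes | not listed |
| Death | yes, any | not listed | yes |
| Rate at 1 year | target at least 60% success | 50% success | 50% failure |

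Neither historical column matches the trial column.

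**Inputs.** Historical n = 46 and rate 50% (section 5.4); cohort A n = 65 (section 24.2); target 60% (section 4). The 50% cannot be re-derived, because no counts by component are given. It is consistent with 23/46, which I use. The documents call it a cumulative incidence, so treating it as a simple proportion without censoring is an assumption.

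**Precision of the benchmark.** The exact 95% interval for 23/46 is 34.9% to 65.1%, so 60% lies inside it. For 39/65 = 60% the interval is 47.1% to 72.0%, which includes 50%.

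**Re-scoring.** Let k be the historical failures due to moderate chronic GVHD alone, and m the historical successes that the trial would fail (alive after relapse, or an uncounted death). Then

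re-scored rate = (23 + k − m)/46.

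The documents give neither k nor m; the values below are assumed. The second figure in each cell is the binomial probability of at least 39 successes in 65 when the true rate equals the re-scored benchmark, that is, with no treatment effect.

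| | k = 2 | k = 5 | k = 8 |
|---|---|---|---|
| m = 0 | 25/46 = 54.3%; 21.5% | 28/46 = 60.9%; 61.0% | 31/46 = 67.4%; 91.8% |
| m = 2 | 23/46 = 50.0%; 6.8% | 26/46 = 56.5%; 33.2% | 29/46 = 63.0%; 74.0% |
| m = 4 | 21/46 = 45.7%; 1.4% | 24/46 = 52.2%; 12.7% | 27/46 = 58.7%; 46.8% |

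**Break-even.** 60% of 46 is 27.6, so 28 successes are needed, and the benchmark reaches the target when k − m is at least 5 (5/46 = 10.9% of the series).

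**The 25% in section 5.3.** If it refers to this composite, a relative gain gives 50% × 1.25 = 62.5% and an absolute gain gives 50% + 25 points = 75%. The 60% target is a 20% relative gain (60/50 = 1.20).

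**The case against.** The strongest reply is that no passage says 60% was derived from 50% or will be tested against it. The composite is secondary, unpowered and has no decision rule. That is correct, and the comparison is an inference. It is a strong one. The objective is worded as an increase, section 5.3 refers to historical controls, and the 50% appears in the section that justifies this endpoint. The other historical rates, 62% for CLL and 52% for MCL, are one-year PFS. If 50% is not the comparator, the 60% has no stated basis.

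Second, the net direction is unknown, and k and m have no source in the documents. This stands. The table illustrates sensitivity and does not measure bias. In its lower-left corner the 60% target is demanding rather than lenient.

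Third, the two historical descriptions may be shorthand for one endpoint, since they are complementary figures from the same 46 patients and the figure itself is not shown. That is possible. Correcting the wording would then settle that part, but both descriptions say moderate to severe, so the chronic GVHD mismatch would remain.

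Fourth, severe-only is a reasoned choice, which section 5.4 ties to high non-relapse mortality. I agree, and the trial definition need not change.

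Finally, re-scoring has limits. Section 5.4 cites a 2005 NIH consensus paper, section 20 specifies 2015 forms for the trial, and the version applied to the 46 patients is not stated. Selection also matters. Section 10 bars ibrutinib after progression or second-line systemic therapy for acute GVHD, and both are composite failures. These points affect how the re-scoring is done. They do not remove the need for it.

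**Conclusion.** The concern holds. The trial composite and its only benchmark use different chronic GVHD thresholds, the benchmark is described in two ways that disagree, and nothing in section 24 reconciles them. With 50% taken as 23/46, a net shift of five patients would place history at the target. Over the assumed range the re-scored rate runs from 45.7% to 67.4%, and the chance of meeting 60% with 65 evaluable patients and no effect runs from 1.4% to 91.8%. Those figures rest on assumed k and m, and the net direction cannot be known without re-scoring. The mismatch itself needs no assumption. The sponsor should correct this before the composite is interpreted. It does not touch the primary PFS analysis or the sample size.

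**What to change.** 1. State which definition produced the 50%, and make section 5.4 and the Figure 2 caption agree.
2. Re-score the 46 patients with the trial's exact composite (second-line acute GVHD therapy, NIH severe chronic GVHD, progression or relapse, any death). Report the rate with its 95% interval and the NIH criteria version used. Restate or justify the 60% from it in sections 1, 4 and 5.4.
3. Also report the trial composite with moderate-to-severe chronic GVHD as failure, which is like for like on that component. The grading is already collected: section 20 says "NIH 2015 diagnosis and scoring forms will be used".
4. State the analysis set for the composite. Section 19 says that, for a participant who does not start within the allowed time, "the participant's registration on the study will be canceled", whereas a footnote to the section 22.1 table says "The End of Study visit should be completed even for patients who withdraw from study without initiating Ibrutinib". Apply the day 60–90 criteria to the historical patients only if the trial composite is analysed in those who start ibrutinib and the old records hold the data. Otherwise leave the 46 unrestricted.
5. Say whether the 25% in section 5.3 refers to this composite or to PFS, and align it with the 60%.

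The cost is a re-tabulation of 46 existing records, one extra summary row and wording changes, with no new data collection in the trial. It will be more work if the older records do not separate moderate from severe. The downside is that the benchmark may move, probably upward on the chronic GVHD component, which would make the target harder. It also stays imprecise at n = 46. Items 2 and 3 matter most; items 1, 4 and 5 are clarifications.
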